6.3.1 Safety Analysis

Safety will be monitored by adverse events reporting. The frequencies of AEs by type, body system, severity and relationship to study supplement will be summarized. SAEs (if any) will be described in detail.

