- Administer MBT study meal (breakfast)
- MBT – hourly blood sample for 8 hours
- After hour 6 a low fat study lunch
- Anthropometry (height, weight, skinfolds, circumferences)
- Whole body DXA (CP Cohort only)
- Spot stool sample will be collected for Fecal Elastase I (CP Cohort only)

-
- Questionnaires: Home Environment (Visit 1), Health History and medications, Quality of life questionnaire (MOS SF-36), PROMIS Survey, Adherence, Adverse Events (Visit 2)
 - Instructions will be given for collection and shipping for: stool collection (72-hour fecal fat analysis and bomb calorimetry), 3-day weighed food records, and adverse events diary
 - Prescribe Creon36™ and dispense to subjects with CP (CP Cohort only)
-

Day 5 - Home

- Maintain adverse events diary
-

Day 6 - Home

- Moderate fat diet
 - 3-day weighed food record begins
 - Food record – Day 1
 - Maintain adverse events diary
-

Day 7 - Home

- Moderate fat diet
 - Food record – Day 2
 - Stool collection begins (72-hour and bomb calorimetry), store frozen until brought to CHOP.
 - 72-hour stool – Day 1
 - Maintain adverse events diary
-

Day 8 - Home

- Moderate fat diet
 - Food record – Day 3
 - 72-hour stool – Day 2
 - Maintain adverse events diary
-

Day 9 - Home

- Moderate fat diet
 - 72-hour stool – Day 3
 - Maintain adverse events diary
-

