Home Environment and Health Questionnaire: The questionnaire will be administered via interview by the research staff, and will consist of two sections. The Health History section has general questions about the subject's health history including documentation of medical history, recent hospital admissions and illnesses, medication, history of pancreatic enzyme supplementation, and nutrient supplement use. A Home Environment section describes aspects of environment, such as education and income level, whether on Medicaid/Medicare and household size to describe the demographic characteristics. In addition to subjects' contact information (name, address, phone numbers); contact information from two additional contacts will be collected to maintain contact with the subject in the event that the subject cannot be contacted at their primary residence.

Quality of Life Questionnaires: In order to assess the health-related quality of life (QOL), validated questionnaires will be administered to all subjects at Visit 1. For all subjects, the Medical Outcomes Study 36-Item Short-Form Health Survey (MOS SF-36), a standardized, validated healthy survey will be administered. The MOS SF-36 covers physical functioning, bodily pain, general health perception, vitality, social functioning, emotional and mental health domains^{32, 61-65}.

Patient Reported Outcomes (PROMIS): We will assess patient reported outcomes at every study visit using the following NIH developed PROMIS short forms: pain, fatigue, depressive symptoms, physical function – mobility, physical function – upper extremity, and peer relationships.

Adherence: Adherence to pancreatic enzyme medication for subjects with CP will be assessed at study Visit 2 and by phone calls. This time will also be used to trouble-shoot any barriers to adherence, and also to collect information on adverse events experienced during the course of the study.

Adverse Events Diary: Subjects will be asked about all adverse events at both Visit 1 and Visit 2, and asked to rate by intensity (mild, moderate, severe). Serious adverse events will be reported as per various policies in a timely manner to CHOP IRB, and CTRC.

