8.3 Definition of an Adverse Event

An adverse event is any untoward medical occurrence in a subject who has participated in the research protocol. The occurrence does not necessarily have to have a causal relationship with the research activities. An AE can therefore be any unfavorable or unintended sign (including an abnormal laboratory finding, for example), symptom, or disease temporally associated with the use of a medicinal product, whether or not considered related to the research activities.

All AEs (including serious AEs) will be noted in the study records and on the case report form with a full description including the nature, date and time of onset, determination of non-serious versus serious, intensity (mild, moderate, severe), duration, causality, and outcome of the event.

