9.4.2 Risk Assessment

The most common side effects associated with taking the pancreatic enzyme Creon36™ in clinical trials were abdominal pain, hyperglycemia, hypoglycemia, frequent abnormal bowel movements, flatulence, vomiting, dizziness, sore throat and cough. Irritation of the inside of the mouth may occur if Creon36™ is not swallowed completely. Increase in blood uric acid levels (hyperuricemia), and severe allergic reactions (pork allergy) including trouble with breathing, skin rashes or swollen lips, although rare, may occur. Although it has never been reported, it is possible for a person to get a viral infection from taking pancreatic enzyme products that come from pigs. Fibrosing colonopathy and colonic strictures is a rare, serious adverse reaction associated with chronic high-dose pancreatic enzyme use over a prolonged period of time with enzyme doses in excess of 6,000 LU/kg body weight per meal or 10,000 LU/kg/day in patients with cystic fibrosis. The dose of Creon36™ prescribed for this study is a maximum of 324,000 LU/day. For an adult weighing 60 kg, this dose is 5,400 LU/kg/day or about half this amount. For an adult weight 40 kg, this daily dose is 8,100 LU/kg/day, still well below. An adult would have to weigh <33 kg (73 lbs.) to match or exceed the 10,000/kg/day dose that is considered excessive.

There are risks associated with discontinuing pancreatic enzyme medication for people with pancreatic insufficiency or reduced pancreatic function resulting in fat malabsorption. These include feelings of indigestion, stomach cramping after meals, gas, foul smelling, floating stools,

light-colored, orange or yellow stools, frequent or loose stools, or weight loss. Some participants in the study may be at increased risk for these symptoms.

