- The participants receiving pancreatic enzyme medication prior to enrolling in the study who will discontinue use prior to the first study visit (Visit 1) may be at risk for signs and symptoms of fat malabsorption (described above) for nine days of the study. These nine days include the three days prior to study Visit 1 (washout period), the day of Visit 1 to CHOP, and the five days of specimen collection after Visit 1. These participants will resume their pancreatic enzyme product and dose for the period of time between the end of the nine days encompassing Visit 1 and the start of the three days prior to Visit 2 when they will switch to Creon 36™. Therefore, they will not be at increased risk for the signs and symptoms of fat malabsorption during the time between visits or during the nine days encompassing Visit 2 as they will be taking pancreatic enzyme medication throughout this period. When the study is completed, these participants will discontinue Creon36™ and resume their usual care and resume their usual pancreatic enzyme product and dose.
- The participants who are naïve to pancreatic enzyme medication prior to entering the study, will take Creon36™ for the nine days encompassing Visit 2 of the study, that is, three days prior to the protocol visit to CHOP, the day of the visit, and then five days after the visit until all specimen collections have been completed. If these participants have undiagnosed reduced pancreatic function and reduced fat absorption, they may have increased risk for the signs and symptoms of fat malabsorption upon discontinuation of Creon36™ at the end of the study. If their pancreatic function and fat absorption is normal, withdrawal from Creon36™ at the end of the study will not increase their risk for these symptoms.

The procedures in this study involve the potential risks related to the drawing of blood. The risks of drawing blood are rare, and minimal. There is a small risk of pain, infection and local irritation associated with insertion of an intravenous heplock catheter. However, this is considered a minimal risk and skilled research staff will insert the intravenous catheter. Each subject with CP will have approximately 100cc (approximately 6-7 Tbsp.) of blood drawn at each study visit. Each healthy subject will have approximately 88cc (approximately 5-6 Tbsp.) of blood drawn at their visit.

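### The adverse event summary has no category or period for the study-required enzyme discontinuation, and the diary omits the first four days of both nine-day blocks

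*Combined protocol and SAP*

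**What the plan says.** Safety reporting consists of one descriptive summary, with any SAEs described individually: "The frequencies of AEs by type, body system, severity and relationship to study supplement will be summarized" (Section 6.3.1, Safety Analysis). Section 5.3 and the synopsis entry on safety evaluations repeat it. None of the three places defines the supplement or mentions cohort, visit or enzyme status.

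The risk section is more specific. Section 9.4.2 states: "There are risks associated with discontinuing pancreatic enzyme medication for people with pancreatic insufficiency or reduced pancreatic function resulting in fat malabsorption". It adds that participants who stop their own enzyme "may be at risk for signs and symptoms of fat malabsorption (described above) for nine days of the study", made up of three days before Visit 1, the visit day and five days after. They then return to their own product until they switch to Creon36 three days before Visit 2.

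Recording is broad. Section 8.3 counts an event "whether or not considered related to the research activities" and says "All AEs (including serious AEs) will be noted in the study records and on the case report form with a full description", covering onset and "intensity (mild, moderate, severe), duration, causality, and outcome of the event". It does not say what causality is judged against. Section 8.4.1 rates each SAE, on five levels, against study activities.

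On enquiry at visits, Section 5.1.3 says "Subjects will be asked about all adverse events at both Visit 1 and Visit 2". The clinic-day list for washout subjects in Section 4.2 instead reads "PROMIS Survey, Adherence, Adverse Events (Visit 2"), which ties the item to the later visit.

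**The concern.** For CP patients already on treatment, the nine days without enzymes are a risk that the study itself imposes and the protocol itself names. The planned summary has no cell for it. If the supplement means Creon36, an event in those nine days precedes any exposure, so an assessor has to call it unrelated even when the protocol caused it. If the term were stretched to the MBT test meal, stopping an enzyme would still not be covered.

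The MBT is put forward as a possible clinical diagnostic test. Anyone who later wants to use it in treated patients will ask how well the washout was tolerated. The summary as specified cannot answer that. Nor does it separate symptoms of stopping an enzyme from side effects of starting Creon36.

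**Working it through.** No power or sample size figure bears on this point, and the plan states none to reproduce. The check sets the sections side by side and counts days.

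**Attribution.** Off-enzyme exposure for a washout subject is 3 + 1 + 5 = 9 days, as Section 9.4.2 says. By the sequence described there, all nine precede the first Creon36 capsule. A non-serious event in that window therefore has one possible entry on the supplement axis: unrelated. The wider study-activities scale in Section 8.4.1 is for SAEs, and Section 8.2 expects none, so foreseeable washout symptoms fall outside it. If the supplement means Creon36, the axis is also empty for the 24 healthy subjects, 24/48 = 50% of the planned sample, because they never take it.

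**Overlap of symptoms.** Section 9.4.2 lists for Creon36 abdominal pain, flatulence and abnormal, frequent bowel movements. For stopping enzymes it lists cramping, gas and loose or frequent stools. These match in pairs. Without a period split they fall into the same rows.

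**Diary and questionnaire**, from the day lists in Sections 4.2 and 4.3:

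| Block | Length | Diary listed | Share | AE questionnaire on clinic day |
|---|---|---|---|---|
| Visit 1, washout CP | 9 days | Days 5-9 | 5/9 = 56% | tagged Visit 2 |
| Visit 2, on Creon36 | 9 days | Days 5-9 | 5/9 = 56% | listed without a tag |
| Visit 1, naive CP and healthy | 7 days | Days 3-7 | 5/7 = 71% | tagged Visit 2 |

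In both nine-day blocks the three pre-visit days and the visit day have no diary: 4/9 = 44%. In the washout list the diary is first explained on Day 4, after the three washout days have passed.

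**Enquiry at Visit 1.** The tag conflicts with three other places. The opening of Section 4.2 says the two visits differ only in the home environment, health history and quality of life questionnaires and fecal elastase, and adds that saliva is taken once. Section 5.1.3 has subjects asked at both visits. Table 1 ticks adverse event monitoring at both CP visits.

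**Size.** The number of CP subjects needing washout is not given. It could be 0 to 24, which is 0 to 24 × 9 = 216 off-enzyme subject-days. No event rate is given either.

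**The case against.** The best defence is that nothing stops these events being recorded. Section 8.3 puts every event on the case report form with its onset date and time. Because Creon36 has a known start, each event can be placed in a period afterwards. The causality entry is not limited to Creon36, SAEs have the wider scale, and Section 6.3.1 does not say that periods or cohorts will be pooled; it is silent. Safety is not an aim, and reporting on 24 CP subjects is descriptive. Most of this stands. It means the fault is one of specification and summary. It does not supply a judgement of relationship to enzyme discontinuation: an onset date gives the period, but causality has no stated reference, and the only one named for the summary is the supplement.

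A reader might go further and infer that events are collected less fully off enzyme, say 5 of 9 days against 9 of 9 on Creon36. That compares diary days alone with diary days plus questionnaire recall. Counted alike, it is 5 of 9 in both blocks by diary, or 9 of 9 in both if Visit 1 enquiry takes place as Section 5.1.3 says. Sections 8.1 and 9.4.1 also promise monitoring throughout the study. It follows that the documents do not support the further inference that Creon36 would look worse than it is.

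A reader might also infer a recall gap of 13 to 36 days for the washout days. That needs the Visit 2 tag to override the other sections, and it uses only the synopsis interval for Visit 2. Section 3.1.3 puts Visit 2 one to two weeks after Visit 1, which gives (7 + 1) to (14 + 3) = 8 to 17 days. The upper end of 36 implies participation of 3 + 1 + 33 + 5 = 42 days, against the four weeks in Section 3.3.1.

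**Conclusion.** The point holds as a defect in how adverse events are attributed and summarised. The single causal axis is undefined and leaves out a risk the protocol names. No cohort or period split is specified, so overlapping gastrointestinal symptoms would not be separated. The diary misses four of nine days in each block equally, and the text on Visit 1 enquiry contradicts itself.

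The documents do not show that washout harm would go unrecorded, or that collection favours one period. The conclusion assumes that the supplement means Creon36, or at least does not include stopping an enzyme, and that the order of periods in Section 9.4.2 is followed. With the number of washout subjects and their event rate unknown, the effect on the safety results cannot be sized. The efficacy comparisons are untouched. The change is worth making because it is cheap and because a causality judgement is hard to reconstruct after the event.

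**What to change.** 1. In Sections 5.3 and 6.3.1 (Safety Analysis), and in the synopsis, record and summarise relationship separately to Creon36, to study-required enzyme discontinuation, and to the MBT or other procedures. State in Section 8.3 that these are the references for causality.
2. Tabulate adverse events by cohort and period (Visit 1 off enzyme, between visits, Visit 2 on Creon36), show washout and naive CP subjects separately, and give the days observed in each.
3. Reconcile the Visit 1 day lists in Section 4.2 with that section's opening paragraph and with Section 5.1.3 on whether the adverse event questionnaire is given at Visit 1.
4. Issue the diary at the in-person consent visit, which Section 4.2 already places before any discontinuation, and start it on Day 1 of each nine-day block.

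The cost is one more causality field on the case report form, some wording, and four more diary days per nine-day block: eight for a washout subject, four for a naive CP subject. No visit is added, and nothing in the dosing or the washout changes. The downside is slightly more diary burden.

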6.4 Sample Size and Power

Sample Size Considerations: The primary hypotheses of this study: 1) the MBT, CFA and BC methods will detect differences in fat absorption between healthy subjects and subjects with CP when they are pancreatic enzyme medication -naive; and 2) the MBT, CFA and BC methods will detect changes in fat absorption with pancreatic enzyme medication administration in the CP cohort. For the MBT method, the sample size selected for the CP cohort ($n=24$) and the healthy comparisons ($n=24$) is based upon our previous experience in CF with detecting differences in C_{max} and AUC for HA and the HA/PA ratio⁴⁹, and in detecting the percent change in HA absorption (from pharmacokinetic modeling) compared to healthy subjects⁵⁰. For the CP vs. healthy comparison, 22 subjects in each group will have 80% power to detect a difference in means of 0.60 (the difference in C_{max} (in AUC)

HA/PA ratio between health group mean of 1.62 (1.30) and CP group mean of 1.02 (0.70)), which is 37% decrease in C_{\max} and 46% decrease in AUC from health group to CP group, assuming that the common SD is 0.68 using a t-test with $\alpha = 0.05$.

For the CFA% outcome, our experience has been in CF and PI, with average CFA% of $81 \pm 14\%$ in one study⁶⁷ and $83 \pm 10\%$ in another⁷¹ when subjects were on pancreatic enzyme medication. In comparison, in healthy subjects, CFA% is typically $\geq 93\%$. From the literature for CP, a number of clinical trials have used CFA% to describe fat malabsorption in subjects with CP and confirmed pancreatic insufficiency before and after administration of pancreatic enzyme medication. Ramesh et al¹⁵ found an increase in CFA% from 66.7 ± 14.0 before pancreatic enzyme medication to $88.9 \pm 5.2\%$ after pancreatic enzyme medication (change of $22.7 \pm 12.2\%$) in adults with CP from India. Also in adults from India participating in a placebo-controlled trial, Thorat et al¹⁶ saw CFA% increase from 66.5 ± 14.1 to $86.1 \pm 7.5\%$ in those taking pancreatic enzyme medication compared to an increase from 67.0 ± 14.0 to $72.9 \pm 11.5\%$ for placebo, a treatment effect of 13.7% (95% CI: 9.1, 18.2) after one week of pancreatic enzyme medication. From this combined experience with variability of the CFA% in both CF and CP, 21 subjects in each group will have 80% power to detect a difference in means of 10% (the difference in CFA% between health group mean of 95% and CP group mean of 85%) assuming that the common SD is 11% using a t-test with $\alpha = 0.05$.

For the BC method, there is limited information for typical variability in calories lost in stool in either healthy subjects or those with malabsorption diagnoses. Using 72-hour stool assessments, Wierdsma et al⁷⁰ has recently reported average daily energy loss of 213 ± 66 kcal in 23 healthy adults. This loss was less in those >50 years old (197 ± 49 kcal). If we assume that approximately 200 kcal/day are lost in the stool of healthy subjects, 21 subjects in each group will have 80% power to detect a difference in means of 50 kcal (the difference in BC between health group mean of 200 and CP group mean of 250 kcal lost in stool) assuming that the common SD is 56 using a t-test with $\alpha = 0.05$.

For the paired comparisons within the CP cohort before and after pancreatic enzyme medication use, 22 subjects will have 80% power to detect a difference in means of 0.44 (C_{\max} HA/PA ratio changes from 1.02 to 1.46 or AUC HA/PA ratio of 1.7 to 1.14), assuming a SD of differences of 0.68, using a paired t-test with $\alpha = 0.05$ two-sided significance level. We have demonstrated that differences of this magnitude in MBT outcomes (exposure metrics) indicating the degree of fat absorption between groups and with varying treatment regimens, are significant when samples of 16 subjects or less have been compared. We acknowledge that PA and HA absorption is moderately variable within subjects with CF and PI^{49, 50}. Between-observation variability was estimated to be 45.3% and 31.9% for PA and HA, respectively⁵⁰. For CFA%, from the literature on CP, the change in CFA% for subjects with CP and confirmed PI before and after pancreatic enzyme medication administration has ranged from 8 to 23% with the SD of that change ranging from 12 to 18%, but averaging at 14%. For CFA%, 22 subjects will have 80% power to detect a difference in means of 9% (increase in CFA% from 85 to 94% after pancreatic enzyme medication administration), assuming a SD of differences of 14%, using a paired t-test with $\alpha = 0.05$ two-sided significance level. For BC, 22 subjects will have 80% power to detect a difference in means of 36 (decrease from 250 to 214 kcal/day in the stool), assuming a SD of differences of 56, using a paired t-test with $\alpha = 0.05$ two-sided significance level.

We expect no more than 10% attrition in this study given a relatively short time period between first and second protocol visits. By enrolling 24 subjects in each group (CP and healthy), we can

account for attrition and also allow for the possibility of greater variability in the MBT, CFA% and BC outcomes within the CP cohort for which we have had no previous experience.

6.5 Interim Analysis

No interim analysis is planned.

7 STUDY MEDICATION

7.1 Description

CREON (pancrelipase) Delayed-Release Capsules 36,000 USP units of lipase (Creon36™), a pancreatic enzyme preparation, is a drug that requires prescription for use. It is approved for use, including the current indication and dosage, by the FDA.

7.1.1 Packaging

Creon36™ capsules containing 36,000 lipase units (LU) each will be provided (AbbVie, Inc.) to subjects with chronic pancreatitis. An 11 day supply of Creon36™ (one bottle or 100 capsules for approximately nine capsules/day) will be provided for nine days of use (81 capsules). Subjects will return unused capsules to the study team at the end of the study, and will be provided with mailing envelopes for this purpose.

7.1.2 Labeling

Storage will be at CHOP North Campus in room temperature (below 77° F) and dry conditions (humidity less than 70%). This facility is temperature controlled and continuously monitored.

7.1.3 Dosing

Participants will take two Creon36™ capsules (72,000 lipase units[LU]) at each meal for three meals a day, and one Creon36™ capsule (36,000 LU) with each snack up to three snacks a day for a total of nine capsules/day or 324,000 LU/day.

